of life, presumably due to protection afforded by maternal antibodies. Following 2 months, the agespecific incidence of clinical episodes of malaria increases to levels near that of the second year of life (see Section D, Study Site). Thus cohort 1 should be essentially free of parasitemia during the first 5 months of age, cohort 2 will be exposed to Pf parasites until 5 months of age, and then not exposed until approximately 10 months and cohort 3 will have continuous exposure. Since SP and AS does not affect pre-erythrocytic stage exposure, all children will have pre-erythrocytic stage exposure continuously. Therefore, it is the degree of exposure to erythrocytic stage antigens that is the independent variable manipulated by the intervention. We have chosen to administer the chemoprohylaxis at 2,5 – 10,5 months and not at 2-10 months of age to avoid possible interactions between the SP+AS treatment and the responses to the EPI vaccines. The SP+AS treatment will be administered 15 days prior to the EPI vaccines (which are administered at 0, 2, 3, 4 and 9 months of age), a sufficient time lag to avoid such interactions. (Amended 15 October, 2004) (Amended 2 December, 2004) (Amended 10 August, 2005)

For our primary outcome variable, we will compare the risk of having at least one malaria episode **as detected by passive case detection** between 12-24 months in the three cohorts. We have chosen our primary outcome variable and follow-up period (12-24 months) in order to duplicate the parameters from the two previous clinical trials upon which this study is based [1, 2]. We anticipate that Cohort 2, with exposure to blood stage antigens blocked during the latter half of infancy, will have a statistically significantly higher risk of at least one episode of malaria between 12-24 months of age than will Cohorts 1 and 3, and that by the same measure, Cohorts 1 and 3 will be similar to each other in terms of risk. Because we are aware that an affect on clinical outcome could be seen even after year two, we will also include follow-up during year three consisting of home visits every 3 months. Children will continue to have full access to both the llha Josina **Maragra** Health Center and Manhiça Hospital for care. In addition, children will be followed long-term for mortality through the demographic surveillance system (DSS) already in place. **(Amended 15 October, 2004) (Amended 2 December, 2004)**

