The three cohorts are proposed in order to address the **central hypothesis**: Exposure to Pf erythrocytic stage antigens in early infancy does not contribute to the development of naturally acquired immunity to malaria but exposure after 5 months of age does contribute to the development of naturally acquired immunity. Specifically, the three cohorts are needed to address the following:

1- The comparison of Cohort 1 (prophylaxis 2-5 2,5-5,5 months) and Cohort 2 (prophylaxis 5-10

5,5-10,5 months) is the key comparison. During the first 10 months of life, we assume that both Cohorts 1 and 2 will have experienced exposure to Pf blood stage parasites, and therefore Pf erythrocytic stage antigens, since each have been left unprotected by prophylaxis during several months. We recognize that infants in the first 5 months of life are likely to have a greater degree of protection due to maternal antibodies than those who are 5-10 months of age, although there is some controversy with regard to this [72]. Nevertheless, previous data from our study site indicate that there is essentially no malaria in the first two months of life but that after 2 months, the age-specific incidence of clinical episodes of malaria increases to levels near that of the second year of life. We also recognize that younger infants may be kept more covered by their mothers and thus experience less exposure to mosquitoes. Thus, the rate of malaria acquisition in the two cohorts may not be the same. Because this will be an uncontrolled variable that may affect the outcome measures of the

Final protocol: 2nd July 2004 Amendment 1: 15th October 2004 Amendment 2: 2nd December 2004 Amendment 3: 11th July 2005 Amendment 4: 10th August 2005 Amendment 5: 12th September 2006 CONFIDENTIAL

Page 17 of 51

[figure not shown]
study, the effects of the number of episodes of parasitemia will be included in the statistical model used for analysis (see below). (Amended 2 December, 2004)

[figure not shown]

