2- By including Cohort 3, we are attempting to replicate the original observations that led to the formulation of the central [1, 2] – that preventing exposure during the first few months of life (Cohort 1) does not modify the rate at which the infants acquire immunity to malaria as compared to the Control group (Cohort 3). We believe it is necessary to include the Cohort 3 given that we are working in an area of different endemicity from the Tanzanian studies. Cohort 3 is needed in order to measure baseline incidence of parasitemia and clinical malaria episodes and furthermore, it is needed to provide control samples for the immunological assays performed on Cohorts 1 and 2.

Final protocol: 2nd July 2004 Amendment 1: 15th October 2004 Amendment 2: 2nd December 2004 Amendment 3: 11th July 2005 Amendment 4: 10th August 2005 Amendment 5: 12th September 2006

CONFIDENTIAL

CSI/CISM

(Amended 2 December, 2004) (Amended 11 July, 2005)

iv. Case Definition and Detection

Final protocol: 2nd July 2004 Amendment 1: 15th October 2004 Amendment 2: 2nd December 2004 Amendment 3: 11th July 2005 Amendment 4: 10th August 2005 Amendment 5: 12th September 2006 CONFIDENTIAL

Case definition: Any fever upon exam (axillary temperature $\ge 37.5^{\circ}$ C) or history of fever within the prior 24 hours plus the presence of Pf asexual stage parasites of any density will constitute a malaria episode.

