Sample size calculations: All sample size calculations are based on $\alpha = 0.05$ (two-tailed) and B = 0.20. With **n** = **65 78** per cohort, we have 80% power (using a two-tailed test) to detect a relative risk of 2 in Cohort 2 as compared to Cohort 1 for at least one clinical malaria episode in the second year of life and to detect of relative risk of 2 in Cohort 2 as compared to Cohort 3, *assuming an incidence of clinical malaria of 0.4 episodes per person-year at risk*. Because *a priori* we intend to make 3 comparisons (Cohort 1 to Cohort 2, Cohort 1 to Cohort 3, and Cohort 2 to Cohort 3), adjustment of the

Final protocol: 2nd July 2004 Amendment 1: 15th October 2004 Amendment 2: 2nd December 2004 Amendment 3: 11th July 2005 Amendment 4: 10th August 2005 Amendment 5: 12th September 2006 CONFIDENTIAL

Page 25 of 51

p value using the Dunn-Sidak method is necessary. Thus, we consider significant a p-value lower than 0.017. We expect to see similar risks between C1 and C3. We will have 80% power to determine that the relative risk is not greater than 2 between the Cohorts 1 and 3. However, detecting a smaller difference would require much larger sample sizes (i.e. 2074 2413 per cohort to detect a difference of 15%) and is not practical for the purposes of this study. (Amended 15 October, 2004)

We anticipate a 15% 20% loss to follow-up and thus our sample size will be increased accordingly to n = 77 98 per cohort. We will first enroll all infants aged 0-2 months from the Maragra area who are eligible for the study and whose mothers have signed an informed consent. We will then start recruiting pregnant women and enrolling their eligible infants as they are born. The number of pregnant women to be enrolled will depend on the number of infants 0-2 months of age recluted in the community. Because we expect that approximately 25% 20% of the pregnant women initially enrolled will not ultimately be included in the study (due to drop-out or delivery of a baby who is not full-term and healthy) we will enroll 103 122 HIV-negative mothers per cohort or a total of 309 366 increase the number of HIV-negative pregnant women to be enrolled accordingly. Given that our previous data indicates that there are at least 400 births per year in Ilha Josina Maragra, we anticipate no problems in enrolling the required number of volunteers over a one year period. (Amended 15 October, 2004) (Amended 2 December, 2004)

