The primary aim of the study is to determine the effect of timing of exposure to Pf erythrocytic stage antigens during infancy (0 to 5 vs 5 to 10 months of age) on subsequent morbidity due to clinical malaria. The primary outcome variable was chosen as the presence or absence of at least one episode of clinical malaria during the second year of life **as detected by passive case detection**, because current epidemiological data suggests that this outcome is a sensitive, inverse indicator of NAI; when used as the primary outcome variable in studies detailed earlier in this proposal (see background and rationale sections) significant differences were detected between cohorts receiving differing prophylaxis [1, 2]. In the study site, an incidence of **0.4 0.48**-episodes of clinical malaria per person year at risk ([name], personal communication). Thus, as described in the sample size section, each of the three cohorts will be compared to the others in pairwise fashion, with the p value for significance reduced to 0.017 to adjust for the three comparisons. **(Amended 15 October, 2004) (Amended 2 December, 2004)**

However, other variables could also affect the likelihood of experiencing at least one clinical episode during the second year of life, such as number of clinical episodes experienced during the first year of life, regardless of the age at which they occurred. In addition, we believe that immunological responses during the first year of life may potentially explain the differences in susceptibility to clinical episodes during the second year (secondary aim), although other factors, such as host genotype (e.g., presence or absence of sickle cell trait, α -thalassemia or others), the presence of haemoglobin AF, parasite genotype, and possibly maternal immune responses, could also affect the primary outcome variable. Because we do not know which of these many factors will be most closely associated with the outcome, we propose a logistic regression analysis to make this assessment. All of these factors will be used in a multiple logistic regression model, and those with significant associations will be identified. Although it is by no means assured, we hope that one of the immunological measurements (see below) will show a significant association and thus will serve as a positive or negative correlate with NAI. A rationale has been provided regarding the concentration of antibody responses to PfEMP-1 as a likely candidate.

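### The claimed 80% power to show that the Cohort 1 to Cohort 3 relative risk is not above 2 belongs to no planned analysis, because the only planned comparison is a significance test at 0.017

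*Protocol*

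**What the plan says.** The central hypothesis (section D.iii, Rationale for the 3 cohorts) has two halves. The first is a no-effect statement: "Exposure to Pf erythrocytic stage antigens in early infancy does not contribute to the development of naturally acquired immunity to malaria". The second is that exposure after 5 months does contribute. Item 2 of the same rationale includes Cohort 3 partly to check that blocking early exposure (Cohort 1) leaves the acquisition of immunity unchanged relative to control. Section C predicts that "Cohorts 1 and 3 will be similar to each other in terms of risk".

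Section D.ix sets n = 78 per cohort for 80% power to detect a relative risk of 2, at an incidence of 0.4 episodes per person-year. It then applies a Dunn-Sidak adjustment for three comparisons: "Thus, we consider significant a p-value lower than 0.017". For Cohort 1 against Cohort 3 it adds: "We will have 80% power to determine that the relative risk is not greater than 2 between the Cohorts 1 and 3". The next sentence says that detecting a smaller difference would need far more infants.

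The analysis plan (section D.xi.1.a) states that "each of the three cohorts will be compared to the others in pairwise fashion, with the p value for significance reduced to 0.017". No confidence-limit rule, one-sided hypothesis or other criterion for similarity is given. Amendment 5 raises the total to 350 because incidence was lower than expected, and restates no power.

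**The concern.** Determining that a relative risk is not greater than 2 is a non-inferiority statement. It needs a test or confidence limit set against the bound of 2. A two-sided test of no difference answers another question: when it is not significant, the data may still be compatible with a ratio above 2. So the stated power and the stated analysis do not belong together.

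Two features add to this. Tightening the significance level to 0.017 guards against false differences but makes a non-significant result more likely when a real difference exists. And 2 is also the relative risk that section D.xi.1.b predicts for Cohort 2 as a sign of lost immunity. Excluding 2 for Cohort 1 would therefore show less than a doubling, which is weaker than showing no contribution.

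What is at stake is the message on vaccine timing. Section C (Potential implication of the research) calls this the most important implication and ties it to exposure before 5 months not contributing to immunity.

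**Working it through.** **Inputs.** From section D.ix: incidence 0.4, relative risk 2, n = 78 evaluable per cohort, 80% power, two-sided level 0.017 per comparison, 20% loss, 350 participants in total. Primary endpoint (section D.viii): at least one episode in the second year. Constants: z(0.9915) = 2.387, z(0.975) = 1.960, z(0.80) = 0.842. The conversion from rate to risk, p = 1 − exp(−λ), is my assumption (constant rate over one year).

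**1. Where the 80% comes from.** For two Poisson rates, n = (z₁₋α/₂ + z₀.₈₀)² (λ₀ + λ₁)/(λ₁ − λ₀)².
- With λ₀ = 0.4, λ₁ = 0.8 and α = 0.017: (2.387 + 0.842)² × 1.2/0.16 = 78.2.
- Power at n = 78: Φ(0.4/√(1.2/78) − 2.387) = Φ(0.838) = 79.9%.
- The superseded figures still visible in the text fit the same formula at a rate of 0.48: 65.1 (given as 65) and 2,075 for a 15% difference (given as 2,074).
- A two-proportion calculation on the converted risks at 0.05 also gives 79. The fit to the superseded figures and the stated use of 0.017 favour the rate formula. On either reading the 80% is power to *detect* a doubling.
- The current 2,413 for a 15% difference recomputes to about 2,490, which does not affect this point.

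**2. Chance of excluding 2 when the cohorts are truly equal.** This is Φ(ln 2/SE − z), with ln 2 = 0.693.
- Rate ratio: SE = √(2/(nλ)) = √(2/31.2) = 0.253.
- Risk ratio: p = 1 − exp(−0.4) = 0.330; SE = √(2(1 − p)/(np)) = 0.228.

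| n = 78, incidence 0.4 | Rate ratio | Risk ratio |
|---|---|---|
| z = 2.387 (matches 0.017) | Φ(0.351) = 64% | Φ(0.649) = 74% |
| z = 1.960 (two-sided 95%) | Φ(0.778) = 78% | Φ(1.076) = 86% |

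**3. Chance of non-significance at 0.017 when the true ratio is 1.5 (n = 78, incidence 0.4).**
- Rate test, 0.4 against 0.6: 1 − Φ(0.2/√(1.0/78) − 2.387) = 1 − Φ(−0.620) = 73%.
- For risks: 1 − Φ((p₂ − p₁ − 2.387·s₀)/s₁), with s₀ the pooled and s₁ the unpooled standard error.
  - Risk ratio 1.5 (0.330 against 0.495): s₀ = 0.0788, s₁ = 0.0777, giving 62%.
  - Binary endpoint with rate ratio 1.5 (0.330 against 1 − exp(−0.6) = 0.451, a risk ratio of 1.37): s₀ = 0.0781, s₁ = 0.0775, giving 80%. At 0.05 the same calculation gives 66%, so the tighter level adds 14 percentage points.

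**4. After Amendment 5.** 350/3 × 0.8 gives about 93 evaluable per cohort. No revised incidence is stated, so 0.3 and 0.2 below are assumptions. Chance that the upper two-sided 95% limit is below 2 when the cohorts are equal:

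| Incidence | Rate ratio | Risk ratio |
|---|---|---|
| 0.4 | 85% | 91% |
| 0.3 (assumed) | 74% | 80% |
| 0.2 (assumed) | 56% | 60% |

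**The case against.** A reader might infer that a non-significant comparison of Cohorts 1 and 3 will be reported as proof of similarity. The protocol does not say so. Its interpretation section (D.xi.1.b) rests support on a relative risk of 2.0 or more in Cohort 2 against Cohorts 1 and 3, and D.iii calls Cohort 1 against Cohort 2 the key comparison. Similarity of Cohorts 1 and 3 appears only as an expectation. This stands, and it limits the point to a stated power without a matching analysis.

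A reader might also infer that the 80% is badly wrong. It is not: with a two-sided 95% limit and the planning assumptions, the power to exclude 2 is 78% or 86%, either side of 80%. It falls clearly short only at the protocol's own 0.017 level, or if incidence is lower.

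Nor should one scale be singled out to make the test look weak. A true doubling would be missed in 34% of trials if the rate doubles and the endpoint is binary, but in 20% with a rate test and 3% if the risk itself doubles.

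Section D.ix openly says that small differences are out of reach, and a statistical analysis plan, not shown, may add a confidence-interval rule. Neither removes the mismatch, because the protocol itself states the power and the test side by side.

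**Conclusion.** The point holds as a mismatch between a claim and its analysis. The protocol claims 80% power to bound the Cohort 1 to Cohort 3 relative risk at 2, while the planned significance test at 0.017 cannot deliver that bound. The 80% is the power to detect a doubling. The matching power to exclude 2 is 64% to 74% at the 0.017 level and 78% to 86% with a 95% interval, assuming equal cohorts, n = 78, incidence 0.4 and large-sample log-ratio intervals.

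Because a true ratio of 1.5 would be non-significant in 62% to 80% of trials, a non-significant result alone would be weak support for the no-effect half of the hypothesis, and the protocol offers no other criterion for it. This should be fixed, but it is not fatal: the key comparison, the data collected and the sample size are unaffected.

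**What to change.** State in the analysis section that Cohort 1 against Cohort 3 is judged by confidence interval:

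- Claim *less than a doubling* only if the upper two-sided 95% limit of the Cohort 1 to Cohort 3 ratio is below 2; otherwise report the comparison as *inconclusive*. Do not word success as early exposure making no contribution.
- State that a p-value above 0.017 is not evidence of similarity.
- Name the ratio (rate or risk) to which the bound applies, and replace the current power sentence with the power of this test at 350 participants (about 93 evaluable per cohort) and the observed incidence. Until that incidence is given, show the assumed range tabulated above.

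The cost is wording in the sample size, analysis and interpretation sections, with no extra infants or data. The downside is a more limited conclusion on Cohort 1 against Cohort 3, and possibly a lower stated power.

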Data from studies of continuous and intermittent anti-malarial treatment conducted in a malariahyperendemic area of Tanzania also support the concept that there is a critical time period during infancy when acquisition of immunity occurs [1, 2]. The first study [1], conducted in 832 infants, showed that malaria prophylaxis with Deltaprim® provided weekly from 8 to 48 weeks (2-11 months) was effective in reducing the frequency of episodes of severe anemia (0.45 vs. 1.04 episodes per person-year; protective efficacy 60.5% [48.2-69.9]) and of clinical malaria (0.53 vs. 1.34 episodes per person-year; protective efficacy 57.3% [43.0-67.9]) in the first year of life compared with placebo. However, during the second year of life, those children who had received prophylaxis as infants had higher rates of severe anemia and malaria than children who did not receive prophylaxis (relative risks 2.2 [1.3-3.7] and 1.8 [1.3-2.6] respectively).

These children were then followed up until their fourth birthday. The results ([name] et al, submitted for publication) of this extended follow-up indicate that chemosuppressing infants during most of the first year of life leads to an overall slightly increased cumulative rate of uncomplicated malaria by the fourth birthday but that this is not associated with an increase in severe malaria or severe anemia. Indeed, when children were aged 4 years the cumulative rate of severe malaria episodes (rate difference -0.12, 95% CI -0.27-0.03) and that of severe anaemia (rate difference -0.19 (95% CI -0.40-0.01) was lower in the intervention cohort, reassuring us on the benefits of exposure reduction interventions.

These data suggest that malaria chemoprophylaxis administered consistently between 8 and 48 weeks (2 to 11 months), while providing protection against disease in the first year of life, impaired the development of NAI.

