(Amended 11 July, 2005) (Amended 10 August, 2005)

viii. Outcome Variables

1. Clinical outcome variables

a) Primary clinical outcome variable

The experience of having at least one episode of clinical malaria in the second year of life *detected by passive case detection.* (Amended 2 December, 2004)

b) Secondary clinical outcome variables

1. Fever (axillary temperature \geq 37.5° C or a history of fever in the previous 24 hours)

2. Hct during first, second and subsequent malaria infections, and during the **24 months** cross-sectional surveys.

3. Density of parasitemia during first, second and subsequent malaria infections, and during the **24** *months* cross-sectional surveys.

4. Time to first clinical episode during the second year of life *detected by passive case detection*.

5. Number of clinical episodes during the first year of life *detected by active or passive case detection*.

6. Number of clinical episodes during the second year of life *detected by passive case detection*. (Amended 2 December, 2004)

2. Immunological outcome variables

a) Primary immunological outcome variables:

 Anti-*Pt*EMP1 antibodies in peripheral blood, as measured at 0, 5, 10, 12, 15, 20 and 25 2.5, 5.5,
10.5, 15 and 24 months of age. The outcome variable to be compared between the cohorts will be: -Antibody units converted from median fluorescence intensity [31]

2. Level-Magnitude and frequency of cytokines (IFN- γ , IL-10) in peripheral blood in response to *in vitro* stimulation with Pf parasite antigens, as measured at 0, 5, 10, 12, 15, 20 and 25 2.5, 5.5, 10.5, 15 and 24 months of age

3. Ratio of Th1 (IFN- γ , TNF α , IL-12 and IL-2) to Th2 (IL-10, IL-5, IL-4) cytokines in plasma, as measured at 0, 5, 10, 12, 15, 20 and 25 **2.5, 5.5, 10.5, 15 and 24** months of age.

4. Anti-GPI antibodies in peripheral blood as measured at 2.5, 5.5, 10.5, 15 and 24 months of age. The outcome variables to be compared between the cohorts will be: -Antibody units converted from ELISA titre -Antibody units converted from Functional Neutralization Assay.

Final protocol: 2nd July 2004 Amendment 1: 15th October 2004 Amendment 2: 2nd December 2004 Amendment 3: 11th July 2005 Amendment 4: 10th August 2005 Amendment 5: 12th September 2006 CONFIDENTIAL

Page 24 of 51

CSI/CISM

5. Host genetics:

-Presence of homozygote or heterozygote for each particular SNP. -Presence or absence of nominated haplotype for each gene.

(Amended 11 July, 2005) (Amended 10 August, 2005)

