The data recorded during weekly visits by research team members and during trips to the health center initiated by the participants' mothers/guardians will provide a relatively detailed accounting of the number of clinical episodes of malaria throughout the study. Data collected regarding episodes will include vital signs (in particular, axillary temperature **and respiratory rate**), Hct, and parasite genotype. In addition, cross-sectional prevalence surveys will be conducted at several time points, allowing a relative assessment of the prevalence and intensity of parasitemia among the three cohorts. Cross sectional surveys will also provide data on anemia, on the developing immune response and on the presence or absence of Hgb AF (see below) and the 24 months cross-sectional survey will also provide data on anaemia and parasitaemia. (Amended 2 December, 2004)

We will look for differences among cohorts in all of these measures at defined cross-sectional timepoints, and intervening intervals where appropriate, during the course of the first two years of life. For example, we will compare the time to first parasitemia in the three cohorts, following the 10 and 12 month cross-sectional surveys. We will also assess the relationship between these measures and the primary outcome variables (clinical episodes and severe anemia), and thus their ability to predict clinical outcomes during the second year of life. (Amended 2 December, 2004)

2. Immunological data

a) Analytical plan: cross-sectional and prospective

In order to assess the development of protective immunity in infants, we have chosen to measure two different immunological parameters as markers of acquired immunity to malaria: an antibody response

Final protocol: 2nd July 2004 Amendment 1: 15th October 2004 Amendment 2: 2nd December 2004 Amendment 3: 11th July 2005 Amendment 4: 10th August 2005 Amendment 5: 12th September 2006 CONFIDENTIAL

Page 33 of 51

(flow cytometry) and a cellular response (cytokines). Specifically, we will measure the type and quality of immune responses at 7 5 cross-sectional time points, and at the time of clinical episode (acute and convalescent), and will compare these immunological outcomes with the clinical outcome(s) for each cohort and between cohorts. (Amended 2 December, 2004)

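### The sample size of 78 per cohort fits a comparison of episode rates, but the primary comparison uses only whether a child had any episode; at the plan's rates that has about 66% power, not 80%

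*Protocol*

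**What the plan says.** Protocol section D.xi.1.a says the primary outcome was "chosen as the presence or absence of at least one episode of clinical malaria during the second year of life", as found by passive case detection; D.viii.1.a lists the same outcome. Each pair of cohorts is compared, and D.ix adds that "we consider significant a p-value lower than 0.017".

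The count is also collected. D.viii.1.b includes "Number of clinical episodes during the second year of life" as secondary outcome 6, and D.xi.1.c expects a "relatively detailed accounting of the number of clinical episodes of malaria throughout the study".

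With 78 evaluable infants in each arm, D.ix claims that "we have 80% power (using a two-tailed test) to detect a relative risk of 2 in Cohort 2 as compared to Cohort 1"; the event is any second-year episode, and the calculation is described as "assuming an incidence of clinical malaria of 0.4 episodes per person-year at risk". Allowing for 20% loss makes this 98 per cohort. Amendment 5 then raised the total to 350 because incidence in the first year of the study was lower than expected. It gives neither the incidence seen nor a new power figure.

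Section C says the outcome and the 12 to 24 month window were chosen "in order to duplicate the parameters from the two previous clinical trials upon which this study is based". D.xi.1.a adds that the outcome is thought to be a sensitive inverse indicator of naturally acquired immunity, and that it was the primary outcome of those trials.

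**The concern.** The sizing input is a rate of episodes, while the primary comparison keeps only whether the count is zero. If the sizing formula compared rates, the stated 80% does not belong to the analysis that will decide the trial. The cut also bites hardest in the cohort expected to do worse, because repeat episodes are more common there.

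At stake are the key comparison (Cohort 2 against Cohort 1) and Cohort 2 against Cohort 3. A true doubling of the episode rate could miss 0.017 on the primary outcome more often than the plan states, in a trial already enlarged because incidence was low.

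**Working it through.** **Inputs from the Protocol.** Two-sided alpha 0.017 (z = 2.387) and power 80% (z = 0.842), so (2.387 + 0.842)² = 10.42. Rate 0.4 per person-year, relative risk 2, one year of follow-up, 78 evaluable per cohort. After Amendment 5: 350/3 less 20% loss = 93 per cohort.

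**Reproducing the plan's figure.** Two-rate Poisson formula: n = 10.42 × (r1 + r2)/(r1 − r2)².
- 0.4 against 0.8: 10.42 × 1.2/0.16 = 78.2. Stated: 78.
- Superseded 0.48 against 0.96: 10.42 × 1.44/0.2304 = 65.1. Superseded figure: 65.

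Other readings:
- Any-episode proportions 1 − exp(−0.4) = 0.330 and 1 − exp(−0.8) = 0.551, alpha 0.017: 104 per cohort.
- The same proportions at unadjusted alpha 0.05: 78.02, so 79 if rounded up. This comes close, but at 0.48 it gives 69.3, not 65, and it is not the 0.017 level the plan uses.
- Risk ratio of 2 (0.330 against 0.659), alpha 0.017: 47.
- Raw 0.4 against 0.8 as proportions, alpha 0.017: 30.

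Only the rate comparison gives both 78 and 65.

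**What the cut removes.** Under a Poisson model it ignores 1 − 0.330/0.4 = 18% of episodes at the lower rate and 1 − 0.551/0.8 = 31% at the higher. A rate ratio of 2 becomes a risk ratio of 0.551/0.330 = 1.67.

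**Binary power** (two proportions, pooled null variance), n = 78: (0.221 × √78 − 2.387 × 0.702)/0.684 = 0.40, so 66%. At n = 93: 0.67, so 75%.

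**Count power** (Wald test of the log rate ratio, variance (1/m1 + 1/m2 + 2f)/n, where f is the between-child rate variance). With f = 0 and n = 78: 0.693/√(3.75/78) − 2.387 = 0.77, so 78%. At n = 93: 1.07, so 86%. The rate-difference form behind the plan's n gives 80% at 78.

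**Between-child variation.** The Protocol gives no value, so f is an assumed range. For the binary outcome, P(at least one) = 1 − (1 + f·m)^(−1/f). At 0.4 against 0.8, binary / count (gap in points):

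| f | n = 78 | n = 93 |
|---|---|---|
| 0 | 66% / 78% (12) | 75% / 86% (11) |
| 0.5 | 49% / 66% (18) | 57% / 75% (18) |
| 1 | 37% / 57% (20) | 44% / 66% (21) |
| 2 | 24% / 43% (19) | 29% / 51% (22) |

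Simulation of the n = 78 cases agreed within about two points, and rejection under no effect stayed between 0.014 and 0.021 for both tests.

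**Lower incidence.** Amendment 5 gives direction only. At an assumed 0.2 against 0.4 the gap runs from 4.5 points (n = 78, f = 0: 40% / 44%) to 10 points (n = 93, f = 2: 24% / 34%).

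**Repeat episodes.** The figures above let the ratio of 2 hold for every episode. Simulation with 0.4 against 0.8 up to the first episode, and a different ratio afterwards (assumed), at n = 78 and 93 and f from 0 to 1:
- repeat ratio 1.5: the count gains about 0 to 5 points;
- repeat ratio 1.0: the count loses about 11 to 17 points.

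**The case against.** **The binary outcome is deliberate and valid.** It measures whether a child enters the second year protected, and the count and the time to first episode are both already secondary outcomes. This stands. A reader might infer that the primary test is invalid or that data are lost to reporting; neither is so. The issue is efficiency and a mismatch between sizing and analysis.

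**The count is not always stronger.** The hypothesis is that later blood-stage exposure builds immunity, so a Cohort 2 child's first second-year infection may itself narrow the difference. D.xi.2.a expects immune responses to equalise between cohorts by 20 to 25 months. This stands, and it is why the gain is conditional: its sign depends on the biology under study.

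**The stated effect is a relative risk of 2 for at least one episode.** Taken literally (0.330 against 0.659), binary power at 78 is about 97% against 99% for the count, and at 0.2 per year the gap is roughly 5 to 7 points. This is what the words say, but it would need only 47 per cohort and does not explain 78.

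**Precedent.** It is tempting to argue that the earlier trials favour the count because Section A reports figures such as "0.53 vs. 1.34 episodes per person-year". Those are first-year results. The second-year malaria result of the first trial is given as a relative risk of 1.8, and D.xi.1.a says the binary outcome was primary in both trials. Duplicating them does not require the cut here, since the same follow-up yields both measures, but it does not by itself support the count.

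**Logistic regression.** A reader might take this to be the primary test. D.xi.1.a proposes it to find which other factors are associated with the outcome. The loss comes from the binary outcome, whichever test is used.

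**Conclusion.** The concern holds as a mismatch between sizing and analysis. The 78 per cohort corresponds to comparing episode rates, whereas the primary comparison is binary and at those rates has about 66% power at 78 and 75% at 93. Even if 78 came from the binary formula at unadjusted 0.05, power at 0.017 would still be 66%.

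At the plan's incidence the count would add about 11 to 12 points under Poisson variation and about 18 to 22 with the assumed between-child variance; at an assumed 0.2 per year, about 4.5 to 10. These gains rest on reading the relative risk of 2 as a rate ratio and on the cohort effect extending to repeat episodes. The documents do not support saying that the count is better in every case, or that incidence has halved.

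**What to change.** Before unblinding, amend D.viii.1.a and D.xi.1.a so that the primary comparison is the number of passively detected clinical episodes from 12 to 24 months (now secondary outcome 6). Analyse it pairwise at 0.017 by negative binomial regression, or Poisson regression with robust standard errors, with log person-time at risk as offset, and report rate ratios with confidence intervals. Prespecify an analytic rule for when two positive findings count as one episode, with matching time removed from risk; D.iv has none. Excluding an assumed 28 days after each episode leaves count power at 78 at about 76% (Poisson). Keep at least one episode as the first supportive analysis.

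If the sponsor prefers the binary outcome, for instance because the effect is expected mainly on first episodes, keep it and correct D.ix: at the plan's rates its power is about 66% at 78 and 75% at 93, and 80% needs 104 evaluable per cohort.

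Either route costs wording only, with no extra infants, visits or samples. Changing the primary outcome also means recording that the decision was made blind to cohort, since low overall incidence was already known, and accepting the risk that the count is weaker if the effect fades after the first episode.
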